7.7.2. Allowable Medications and Therapies

The following medications and therapies are allowed:

• Empirical antibiotic treatment for secondary bacterial infections is allowed during the course of study.

[figure not shown]
7.8. CLINICAL LABORATORY ASSESSMENTS

Laboratory samples will be collected for analysis of the following parameters described in Table 7-1.

- Biochemistry, Complete Blood Count (CBC), Coagulation indices and Urinalysis: At Screening (V1), V10, and V17 (EOT).
- CD4+ and CD8+ T cell count: At V2, V10, and V17 (EOT).
- Serum cytokine and chemokine levels: At V2, V10, and V17 (EOT).
- CCR5 Receptor Occupancy: At V2, V10, and V17 (EOT).
- Immunophenotypic Biomarker Analysis: At V2, V10, V17 (EOT), and V18 (FU).
- Urine pregnancy test (for female subjects of childbearing potential): At Screening (V1), V2, V10, and V17 (EOT).

All laboratory reports will be reviewed by the Investigator. Abnormal results that are considered by the Investigator to be clinically significant will be recorded as adverse events. If in the Investigator judgment, in order to make the determination of clinical significance the testing may be needed to

CONFIDENTIAL Page 64 of 101

be repeated. Validated, quality-controlled laboratory data will be transferred to the main database for analyses.

Table 7-1: Lab Parameters

CBC Parameters	Biochemistry Parameters	Urinalysis			
Hemoglobin (g/dL)	Liver Function Tests	pН			
Hematocrit (%)	Total bilirubin (mg/dL)	Specimen Appearance			
RBC/Erythrocytes (10^12/L)	Alkaline Phosphatase (ALP)	Color			
WBC/Leukocytes (10^6/L)	(U/L)	Specific Gravity			
Absolute Neutrophil Count	Aspartate Aminotransferase	Ketones			
(10^6/L)	(AST) (or SGOT) (U/L)	Bilirubin			
Platelets (10^9/L)	Alanine Aminotransferase (ALT)	Occult Blood			
Differential WBC:	(or SGPT) (U/L)	Glucose			
- Neutrophils (%)	Total Protein (g/dL)	Protein			
- Lymphocytes (%)	Albumin (g/dL)	Nitrite			
- Monocytes (%)	Lactate Dehydrogenase (U/L)	Urobilinogen (mg/dL)			
- Eosinophils (%)	Renal Function Tests	Leukocyte Esterase			
- Basophils (%)	Serum creatinine	Leukocytes(/HPF)			
Miscellaneous	eGFR Electrolytes	Cytokine and Chemokine Panel			
Urine pregnancy test	Sodium (mEq/L)	sCD40L, EGF, Eotaxin (CCL11),			
(for female subjects of childbearing	Potassium (mEq/L)	FGF-2, Flt-3 ligand, Fractalkine, G-			
potential)	Chloride (mEq/L)	CSF, GM-CSF, GRO alpha (CXCL1),			
CD4+ and CD8+ T cell count		IFN-alpha2, IFN-gamma, IL-1 alpha,			
CD4: and CD6: I cen count	Calcium (mg/dL)				
CCR5 receptor occupancy	Calcium (mg/dL) Bicarbonate (mEq/L)	IL-1 beta, IL-1RA, IL-2, IL-2R, IL-3,			
	/	IL-1 beta, IL-1RA, IL-2, IL-2R, IL-3, IL-4, IL-5, IL-6, IL-7, IL-8 (CXCL8),			
CCR5 receptor occupancy	Bicarbonate (mEq/L)	IL-1 beta, IL-1RA, IL-2, IL-2R, IL-3,			
CCR5 receptor occupancy Immunophenotypic biomarker	Bicarbonate (mEq/L) Other:	IL-1 beta, IL-1RA, IL-2, IL-2R, IL-3, IL-4, IL-5, IL-6, IL-7, IL-8 (CXCL8), IL-9, IL-10, IL-12 (p40/p70) IL-13,			
CCR5 receptor occupancy Immunophenotypic biomarker	Bicarbonate (mEq/L) Other: Glucose, Random (mg/dL)	IL-1 beta, IL-1RA, IL-2, IL-2R, IL-3, IL-4, IL-5, IL-6, IL-7, IL-8 (CXCL8), IL-9, IL-10, IL-12 (p40/p70) IL-13, IL-15, IL-17A, IL-17E/IL-25, IL-17F,			
CCR5 receptor occupancy Immunophenotypic biomarker	Bicarbonate (mEq/L) Other: Glucose, Random (mg/dL) Cholesterol, Total (mg/dL)	IL-1 beta, IL-1RA, IL-2, IL-2R, IL-3, IL-4, IL-5, IL-6, IL-7, IL-8 (CXCL8), IL-9, IL-10, IL-12 (p40/p70) IL-13, IL-15, IL-17A, IL-17E/IL-25, IL-17F, IL-18, IL-22, IL-27, IP-10 (CXCL10),			
CCR5 receptor occupancy Immunophenotypic biomarker	Bicarbonate (mEq/L) Other: Glucose, Random (mg/dL) Cholesterol, Total (mg/dL) Creatine kinase,	IL-1 beta, IL-1RA, IL-2, IL-2R, IL-3, IL-4, IL-5, IL-6, IL-7, IL-8 (CXCL8), IL-9, IL-10, IL-12 (p40/p70) IL-13, IL-15, IL-17A, IL-17E/IL-25, IL-17F, IL-18, IL-22, IL-27, IP-10 (CXCL10), MCP-1 (CCL2), MCP-3, M-CSF, MDC (CCL22), MIG (CXCL9), MIP-1 alpha (CCL3), MIP-1 beta (CCL4),			
CCR5 receptor occupancy Immunophenotypic biomarker	Bicarbonate (mEq/L) Other: Glucose, Random (mg/dL) Cholesterol, Total (mg/dL) Creatine kinase, C-reactive protein	IL-1 beta, IL-1RA, IL-2, IL-2R, IL-3, IL-4, IL-5, IL-6, IL-7, IL-8 (CXCL8), IL-9, IL-10, IL-12 (p40/p70) IL-13, IL-15, IL-17A, IL-17E/IL-25, IL-17F, IL-18, IL-22, IL-27, IP-10 (CXCL10), MCP-1 (CCL2), MCP-3, M-CSF, MDC (CCL22), MIG (CXCL9), MIP-1 alpha (CCL3), MIP-1 beta (CCL4), PDGF-AA, PDGF-AB/BB, RANTES			
CCR5 receptor occupancy Immunophenotypic biomarker	Bicarbonate (mEq/L) Other: Glucose, Random (mg/dL) Cholesterol, Total (mg/dL) Creatine kinase, C-reactive protein Serum ferritin	IL-1 beta, IL-1RA, IL-2, IL-2R, IL-3, IL-4, IL-5, IL-6, IL-7, IL-8 (CXCL8), IL-9, IL-10, IL-12 (p40/p70) IL-13, IL-15, IL-17A, IL-17E/IL-25, IL-17F, IL-18, IL-22, IL-27, IP-10 (CXCL10), MCP-1 (CCL2), MCP-3, M-CSF, MDC (CCL22), MIG (CXCL9), MIP-1 alpha (CCL3), MIP-1 beta (CCL4), PDGF-AA, PDGF-AB/BB, RANTES (CCL5), TGF-alpha, TNF-alpha,			
CCR5 receptor occupancy Immunophenotypic biomarker	Bicarbonate (mEq/L) Other: Glucose, Random (mg/dL) Cholesterol, Total (mg/dL) Creatine kinase, C-reactive protein Serum ferritin Coagulation Parameters	IL-1 beta, IL-1RA, IL-2, IL-2R, IL-3, IL-4, IL-5, IL-6, IL-7, IL-8 (CXCL8), IL-9, IL-10, IL-12 (p40/p70) IL-13, IL-15, IL-17A, IL-17E/IL-25, IL-17F, IL-18, IL-22, IL-27, IP-10 (CXCL10), MCP-1 (CCL2), MCP-3, M-CSF, MDC (CCL22), MIG (CXCL9), MIP-1 alpha (CCL3), MIP-1 beta (CCL4), PDGF-AA, PDGF-AB/BB, RANTES			

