1.4.2.5. PRO 140 2301 Study

PRO 140 2301 was a multi-center, randomized, double-blind, placebo-controlled, parallel group study in 30 male and female adult subjects infected with HIV-1 [Jacobson, 2010]. Subjects were randomized to one of three groups (N=10/group), each receiving one of three treatments: (i) a single IV dose of 5 mg/kg by 30-minute IV infusion; (ii) a single IV dose of 10 mg/kg by 30-minute IV infusion; (iii) a single placebo dose by 30-minute IV infusion. The objective of the study was to assess and characterize the PK and PD of PRO 140 administered by IV infusion, assess efficacy at a new dosage level, and safety and tolerability of single doses of PRO 140.

All PRO 140-treated subjects had more than 10-fold reduction in viral loads [Jacobson, 2010]. Both the 5 mg/kg and 10 mg/kg doses have shown favorable tolerability and no dose-limiting toxicity has been observed. High levels of receptor occupancy (>85% reduction in the number of cells detected) were observed for 29 days after treatment with both 5 and 10 mg/kg doses.

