8.2.3. Exploratory Outcome Measures (Endpoints)

- Change from baseline in pulse oxygen saturation (SpO2) at Day 7, 14, 21, 28, 35, 42, 49, and 56.
- Change from baseline in serum cytokine and chemokine levels on Days 28 and 56.
- Change from baseline in CD4+ and CD8+ T cell count on Days 28 and 56.
- Change from baseline in Transgrowth factor beta 1 (TGF beta1) on Days 28 and 56.
- Change from baseline in CRP on Days 28and 56.
- Change from baseline in CCR5 receptor occupancy on Days 28 and 56.
- To explore biomarkers that may predict and/or act as pharmacodynamic indicators of pharmacologic activity of leronlimab.
- Evaluation of Global Health Assessment at Day 56.

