8.2.4. Safety Measures

Safety will be assessed using:

- Incidence of treatment-related adverse events (TEAEs)
- Incidence and severity of treatment-emergent adverse events (TEAEs)
- Incidence of serious adverse events (SAEs)
- Incidence of TEAEs and SAEs leading to discontinuation of study medication.
- Changes in blood chemistry, hematology and coagulation parameter results

CONFIDENTIAL Page 69 of 101

- Changes in vital signs including temperature, pulse, respiratory rate, systolic and diastolic blood pressure
- Changes in physical examination results
- Changes in electrocardiogram (ECG) results

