8.6. BLINDING

All subjects, Investigators and their staff (except unblinded pharmacist or designated site staff), and all Sponsor/CRO personnel involved in the management of the study will be blinded to treatment assignments.

The Amarex Information Technology department will be unblinded to treatment. As noted above, the Amarex Technology department is not otherwise involved with the study.

Treatment unblinding for the study will occur after all clinical data have been received, data inconsistencies have been resolved, and the database is locked, except for safety reasons on a case-by-case basis (i.e., emergency unblinding).

The process for emergency unblinding will be outlined in detail in the Randomization Plan. In addition, any subject that is unblinded for any reason will be identified and discussed in the final clinical study report.

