9.2.3. Causality Assessment

AEs will be assigned a relationship (causality) to the study treatment. The Investigator will be responsible for determining the relationship between an AE and the study treatment. The type of event, organ system affected, and timing of onset of the event will be factors in assessing the likelihood that an AE is related to the study treatment. Relationship of AEs to study treatment will be classified as follows:

- 1. Definitely related: This category applies to those AEs that the Investigator feels are incontrovertibly related to the study treatment. An AE may be assigned an attribution of definitely related if or when it meets all of the following criteria: (1) it follows a reasonable temporal sequence from administration of the study treatment; (2) it could not be reasonably explained by the known characteristics of the subject's clinical state, environmental or toxic factors, or other modes of therapy administered to the subject; (3) it follows a known response pattern to treatment with the study treatment.
- 2. Probably related: This category applies to those AEs which, after careful medical consideration at the time they are evaluated, are felt with a high degree of certainty to be related to the study treatment. An AE may be considered probable if or when (must have three): (1) it follows a reasonable temporal sequence from administration of the study treatment. (2) It could not readily have been produced by subject's clinical state, environmental or toxic factors, or other therapies administered to the subject. (3) Disappears or is decreased upon discontinuation of the study treatment. (4) It follows a known response pattern to treatment with the study

CONFIDENTIAL Page 76 of 101

[†]Self care ADL refer to bathing, dressing and undressing, feeding self, using the toilet, taking medications, and not bedridden.

treatment.

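### Protocol 7.8 gives the blinded investigator all laboratory reports with no exception for CCR5 receptor occupancy, a result that would probably show the arm

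*Combined protocol and SAP*

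**What the plan says.** Protocol 7.8 lists the laboratory tests and their visits. Receptor occupancy is in that list, at V2 (pre-dose baseline), V10 (Day 28) and V17 (Day 56), alongside biochemistry, blood count, coagulation and urinalysis. The paragraph under the list opens "All laboratory reports will be reviewed by the Investigator". It goes on to clinically significant abnormal results, which become adverse events, and to repeat testing. It ends "Validated, quality-controlled laboratory data will be transferred to the main database for analyses".

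Protocol 8.6, repeated in SAP 2.7, applies the blind to "All subjects, Investigators and their staff (except unblinded pharmacist or designated site staff"), and to the Sponsor and CRO personnel who manage the study.

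Occupancy is an exploratory endpoint in Protocol 8.2.3: "Change from baseline in CCR5 receptor occupancy on Days 28 and 56". It is not among the safety measures in 8.2.4, where the laboratory item is "Changes in blood chemistry, hematology and coagulation parameter results".

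On attribution of adverse events, Protocol 9.2.3 says "The Investigator will be responsible for determining the relationship between an AE and the study treatment".

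**The concern.** Receptor occupancy measures how far the antibody's own target is bound. A result from a treated subject should differ sharply from one on placebo, so a blinded person who reads it has in effect been told the arm. A site that follows 7.8 to the letter would hand that result to the investigator.

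The main judgment at stake is causality. In Protocol 5.2, stopping triggers 1 to 3 of 4 depend on relatedness as judged by the treating investigator. The fourth does not name who judges. The Medical Monitor and Lead Principal Investigator then review the data, and the Medical Monitor and Sponsor decide whether the study continues. Section 12 states that a data safety monitoring committee does not apply. Knowledge of the arm could move the first judgment in either direction.

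**Working it through.** The plan states no figure to reproduce. The check is a comparison of sections, followed by simple day counts.

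**1. Is there an exception anywhere?** None of Protocol 7.8, 8.6 and 8.7 or SAP 2.7 and 2.8 withholds occupancy from the investigator. With 50 subjects and two post-dose samples each, full attendance gives 50 × 2 = 100 results within the literal wording of 7.8.

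**2. Would a result show the arm?**
- Protocol 1.4.2.5, on single IV doses of 5 or 10 mg/kg in HIV-1: "High levels of receptor occupancy (>85% reduction in the number of cells detected) were observed for 29 days after treatment".
- V10 is 7 (±1) days after V8, the fourth dose. V17 is 7 (±1) days after V16, the eighth dose. The interval is therefore 6 to 8 days, assuming that V10 blood is drawn before that visit's dose and that no dose was missed. The documents state neither.
- If the one preceding dose was missed, the interval is two visit gaps: 6 + 6 = 12 to 8 + 8 = 16 days. Both ranges are shorter than 29 days.
- Occupancy at 700 mg SC weekly and on placebo is not given. That the result would show the arm is therefore a reasonable inference, not a documented fact.

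**3. How much follow-up comes after the result?** Turnaround is not given, so lags are assumed. Adverse events are reported from the first treatment visit to the final visit (Protocol 9.2), nominally Day 0 to Day 84. The diary covers Days 1 to 56. For the V10 result:
- share of adverse event window = (84 − 28 − lag) / 84
- share of diary days = (56 − 28 − lag) / 56, not below zero

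| Lag (days) | Adverse event window left | Diary days left |
|---|---|---|
| 0 | 56/84 = 66.7% | 28/56 = 50% |
| 7 | 49/84 = 58.3% | 21/56 = 37.5% |
| 14 | 42/84 = 50.0% | 14/56 = 25% |
| 21 | 35/84 = 41.7% | 7/56 = 12.5% |
| 28 | 28/84 = 33.3% | 0 |
| 42 | 14/84 = 16.7% | 0 |
| 56 | 0 | 0 |

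For the V17 result, the adverse event share is (84 − 56 − lag) / 84. That is 33.3%, 25.0%, 16.7%, 8.3% and 0% at lags of 0, 7, 14, 21 and 28 days, with no diary days left. Batch assay after Day 84 gives zero throughout.

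**4. Secondary note: drug records.** Sections 6.1.2 and 6.1.6 name the investigator as keeper of the dispensing log and as the person who returns containers and labels. Sections 6.1.2 and 6.1.7 have the study CRA check the records and kits. Section 6.1 describes kits for the leronlimab arm only, and placebo is saline. The labels in 6.1.1 name PRO 140 and carry a subject number. Against this, 6.1.3 gives syringe preparation to the unblinded pharmacist or designated staff, and 6.1.7 places the records on the site and requires the preparer to be identified. What is missing is a line that assigns kit-level records and returns to that unblinded role.

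**The case against.** The strongest reply is that 7.8 means safety laboratories. The sentences after the review rule concern clinical significance and repeat testing, which have no evident application to occupancy. SAP 8.3.2 describes laboratory evaluations as hematology, biochemistry, serology and urinalysis. No passage says that occupancy results go to sites at all. This stands as a likely account of intent, and it makes the exposure possible rather than shown. It does not remove the problem, because the rule covers every report and sits directly under a list that includes occupancy.

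Three stronger readings are tempting, and the documents do not support them.

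- *A reader might infer that investigators will be unblinded from Day 28.* Neither the timing of reports nor occupancy at this dose and route is given.
- *A reader might infer that the primary endpoint is compromised.* The diary and PROMIS forms are completed by subjects, and 7.8 does not send them the result. Any effect would be indirect, through the investigator.
- *A reader might infer that the drug records unblind the investigator from the first dose.* The date and amount dispensed do not show the arm, unblinded staff prepare the syringes, and the pharmacy manual, which is not part of these documents, may settle the delegation.

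The transfer of laboratory data to the main database is also weak evidence of exposure. Its stated purpose is analysis, and Protocol 14.2 refers data handling to a Data Management Plan that is not supplied.

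**Conclusion.** The point holds as a gap in Protocol 7.8. Read literally, the section gives a blinded investigator an exploratory result that would probably reveal the arm, and no passage prevents it. The conclusion rests on three assumptions: that occupancy at 700 mg SC weekly separates the arms about as well as the earlier IV data suggest, that V10 blood is drawn before dosing with no more than one preceding dose missed, and that results reach sites during the study. If the third fails, there is no exposure. If all hold, up to two thirds of the adverse event window follows the V10 result, and the judgment exposed is the one behind three of the four stopping triggers. In an exploratory trial of 50 subjects this is worth correcting, because the correction is nearly free. It does not show that the blind fails. The drug-record wording is a minor matter of delegation.

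**What to change.** **Main change, Protocol 7.8.** State that in-study investigator review covers the safety laboratories. State that post-baseline CCR5 receptor occupancy is withheld from sites and from blinded Sponsor/CRO staff until the unblinding described in 8.7.2. The review duty would then no longer extend to the other exploratory assays, but the withholding instruction is proposed for occupancy alone. The cost is a few words of protocol text and an instruction to the laboratory. The downside is that sites see an exploratory result later. No listed safety measure is lost.

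**Secondary change, Protocol 6.1.2, 6.1.6 and 6.1.7.** Reconcile these with 6.1.3 and 8.6 by assigning kit-level records and the return of containers and labels to the unblinded pharmacist or designated site staff already named there. The cost is protocol wording and a written site delegation. If the pharmacy manual already does this, a cross-reference is enough.

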7.9. STUDY TREATMENT APPLICATION

Refer to Section 6.1.3 for details.

7.10. Pulse Oxygen Saturation (SpO2)

CONFIDENTIAL Page 65 of 101

Pulse Oxygen Saturation (SPO2) will be measured at Screening and V2 (pre-dose and post-dose), V4, V6, V8, V10, V12, V14, V16, V17 (EOT), and V18 (Follow-Up).

Note: Post-dose values will be recorded at V4, V6, V8, V10, V12, V14, and V16.

7.11. 12-LEAD ELECTROCARDIOGRAM

A resting supine 12-lead ECG will be conducted at the Screening Visit (V1), and Visit 17 (EOT). A 12-lead ECG will be repeated during the study only if clinically indicated and at the discretion of the treating physician. The results will be evaluated by the Investigator. The following parameters will be recorded: ventricular rate (beats per minute), PR interval (msec), QRS interval (msec), QT interval (msec), and QTc interval (msec). Additionally, the Investigator will record the overall results of the ECG reading as either normal or abnormal, and as either not clinically significant or clinically significant. If abnormalities are observed, each will be recorded.

7.12. REQUIREMENT OF HOSPITALIZATION

The incidence and duration, in days, of subjects' hospitalization will be assessed at beginning at V3 through V18 (Follow-Up).

7.13. RANDOMIZATION

Subjects who are eligible to participate in the trial will be randomized to one of the treatment groups via IWRS (Interactive Web Based Randomization System) at Visit 2 prior to IP administration. The randomization will be central with a 1:1 ratio of Active Treatment to Control Treatment to ensure even distribution of Active and Control subjects.

7.14. CLINICAL SYMPTOM SCORE

Clinical symptom score will be assessed at Screening (V1) and baseline (V2) based on following commonly reported symptoms consistent with COVID-19 infection for a prolonged period of time (>12 weeks):

- Respiratory symptoms such as cough, sore throat, stuffy or runny nose, shortness of breath (difficulty breathing), tightness of chest etc.
- Neurological symptoms such as difficulty in concentration (brain fog), sleep disturbance/insomnia, headache, dizziness, anxiety, tingling or numbness, loss of sense of smell or taste.
- Cardiovascular and Gastrointestinal symptoms such as feeling of fast heartbeat, nausea, vomiting, diarrhea.

CONFIDENTIAL Page 66 of 101

- Musculoskeletal symptoms such as muscle aches/cramps, muscle weakness, joint pain/swelling.
- General immune response symptoms such as fatigue (low energy or tirednesschills or shivering, feeling hot or feverish or exertional malaise (feeling of discomfort, illness, or lack of well-being after physical activity or mental stress).

Note: Clinical Symptom Score is obtained from the patient diary (refer to Appendix 1 for scoring instructions).

7.15. PATIENT SYMPTOM DIARY

After receiving treatment, subjects will be given a diary to record all symptoms daily throughout the entire treatment period. See Appendix 1.

7.16. PROMIS® FATIGUE SCALE

This score is based on questions focused on physical fatigue and psychological fatigue. The assessment will be performed (self-administered by the subject) at V2, V4, V6, V8, V10, V12, V14, V16, and V17 (EOT). See Appendix 3.

7.17. PROMIS® COGNITIVE FUNCTION

The brief mental fatigue questionnaire evaluates subject cognitive symptoms. The assessment will be performed (self-administered by the subject) at V2, V4, V6, V8, V10, V12, V14, V16, and V17 (EOT). See Appendix 4.

7.18. PROMIS® SLEEP DISTURBANCE

The brief questionnaire evaluates subjects' sleep quality. The assessment will be performed (self-administered by the subject) at V2, V4, V6, V8, V10, V12, V14, V16, and V17 (EOT). See Appendix 5.

7.19. GLOBAL HEALTH ASSESSMENT

The brief questionnaire evaluates general health (physical and mental health) and quality of life. This is an exploratory (non-validated) assessment developed (based on PROMIS® Scale v1.2 – Global Health) with an intent to assist in identifying more appropriate global health measurement for the future studies in long-hauler COVID-19 population and will not be used for labeling claims. The assessment will be performed (self-administered by the subject) at V17 (EOT/Day 56). See Appendix 6.

CONFIDENTIAL Page 67 of 101

8. STATISTICAL ANALYSIS

This section presents general information about statistical considerations and concepts and a brief discussion on analysis methodology, as well as some data conventions. Detailed descriptions of the statistical analysis methods and data conventions that will be used in this study will be in a separate document; i.e., the Statistical Analysis Plan (SAP).

8.1. TREATMENT GROUPS

There will be two treatment groups in the study:

- Leronlimab (PRO 140) 700 mg
- Placebo

8.2. DESCRIPTION OF STUDY OUTCOMES (ENDPOINTS)

8.2.1. Primary Endpoint

The primary endpoint for the study is:

• Changes from baseline in daily COVID-19-related symptom severity score through day 56 Note: A set of common COVID-19-related symptoms (see patient diary template) will be evaluated daily by the patient regardless of which symptoms a subject had at baseline, as new symptoms may appear following the baseline assessment.

